2.1.2 Secondary Objectives

To evaluate and compare effects of MS1819-SD and porcine PERT on other measures of digestion including the coefficient of nitrogen absorption (CNA), stool weight, body weight, body mass index (BMI), signs and symptoms of malabsorption, and serum liposoluble vitamins A, D, E, and K.

2.2 Overall Study Design and Plan

This is a Phase 2, open-label, multicenter, 2x2 crossover study assessing the safety and efficacy of MS1819-SD (2240 mg/day) in patients with EPI due to CF for male and female patients aged 18 years or older. Efficacy will be evaluated by comparing treatment with MS1819-SD to treatment with porcine PERT at the same dose that was being administered during the prestudy period.

MS1819-SD will be assessed in a 2x2 crossover including at least 30 patients completing both periods such that at least 15 patients will complete each sequence of treatments. Patients will be randomized to receive either the sequence consisting of MS1819-SD for 3 weeks followed by PERT for another 3 weeks or the opposite sequence of treatments (PERT for 3 weeks followed by MS1819-SD for another 3 weeks).

The study will not employ a washout period between the first treatment period and the second treatment period. Recent experience with crossover lipase enzyme treatment from commercial PERTs to investigational lipase has demonstrated that symptoms of malabsorption may become evident within a matter of days, indicating little residual carryover effect of the original lipase. Furthermore, the 3-week duration of treatment with either study agent is well established as sufficient to show the degree of lipase effectiveness.

Dosages will typically be fractionated as follows: 1/4 of the daily dose at each 3 main meals, and 1/8 at each of the 2 snacks (ie, 2240 mg/day will be fractionated as follows: 4 capsules of 140 mg with the morning, noontime, and evening meals, plus 2 capsules of

140 mg with the morning and evening snacks). Individual variations may occur as long as total daily dose is achieved.

The dose of prestudy porcine PERT will be the same dose that was being administered during the prestudy period.

Randomized patients will be males and females 18 years or older. The primary efficacy endpoint is the coefficient of fat absorption (CFA) that will be assessed at the end of the 3-week period of treatment for each 2x2 crossover.

A study flow chart is presented in Appendix 13.1, and a schedule of events is presented in Appendix 13.2.

2.3 Study Population

Subjects that are ≥ 18 years of age with EPI due to CF will be enrolled. The inclusion and exclusion criteria for the study are enumerated in Sections 7.3.2 and 7.3.3 of the protocol, respectively.

2.4 Treatment Regimens

At randomization, subjects will be assigned in a 1:1 ratio to receive either the sequence consisting of MS1819-SD for 3 weeks followed by PERT for another 3 weeks or the opposite sequence of treatments (PERT for 3 weeks followed by MS1819-SD for another 3 weeks).

Subjects will receive 2240 mg/day of MS1819-SD while in the MS1819-SD period of their treatment sequence. Subjects will receive the same dose of PERT that was being administered during the prestudy period while in the porcine PERT period of their treatment sequence.

2.5 Treatment Group Assignments or Randomization

Subjects who meet all of the enrollment criteria will be randomized to receive MS1819-SD followed by PERT or PERT followed by MS1819-SD using a 1:1 allocation ratio.

2.6 Sample Size Determination

The primary objectives of the trial are to assess the safety of MS1819 and whether the efficacy of MS1819 is noninferior to porcine PERT. The sample size was primarily selected to be sufficient to address the safety objectives of this trial. Given the sample size, efficacy will be assessed with the understanding that adequate power for assessing efficacy would only be achieved for differences that are more favorable than expected.

With regard to safety assessment, at least 30 patients completing both periods are judged enough to adequately assess safety. Any event not occurring in the study would have a 95% CI on the rate extending from 0% to 10%; thus events not occurring may be assumed to be uncommon in the population (<10%).

With regard to efficacy, the primary objective is to show that the efficacy of MS1819, measured on the primary endpoint (ie, the CFA), is noninferior to porcine PERT.

- The noninferiority is chosen equal to 15% and the rationale for this choice is as follows: the difference in mean change from baseline in CFA between the reference and placebo was found to be approximately 32.6% in Trapnell (2011). According to the guidance on Noninferiority Clinical Trials to establish effectiveness (2016), the noninferiority (NI) margin should preserve a specified fraction of the difference between the reference and placebo. A NI margin of 15% preserves 54% of the estimated difference between the reference and placebo.
- In a recent unpublished trial, the standard deviation of the change in CFA was found to be around 16% among patients with a baseline CFA at or above 80%. As some patients enrolled in this trial might have a CFA under porcine PERT lower than 80%, a higher standard deviation of around 20% is expected.
- Because the patients enrolled in the trial are already stabilized on porcine PERT, it is expected that the difference in CFA means between MS1819 and porcine PERT slightly favors PERT, which is expected to be around -8%.

Out of an abundance of caution, the planned sample size is limited to roughly 30 subjects completing. With regard to safety assessment, 30 patients completing both periods are judged enough to adequately assess safety. However, assuming a standard deviation of 20% for the paired differences in CFA measurements within each patient, a noninferiority margin of 15%, a more favorable than expected difference of -4.0% in CFA means between MS1819 vs porcine PERT that favors PERT, a sample size of 30 patients completing both periods will provide a power of around 80% to show noninferiority of MS1819 to porcine PERT at the 0.05 2-sided nominal 0.05 level of significance (that is, a one-sided alpha of 0.025). Accounting for a 20% dropout rate, 38 patients will be sufficient to achieve a power of at least 80%.

3. GENERAL ANALYSIS AND REPORTING CONVENTIONS

The following is a list of general analysis and reporting conventions to be applied for this study.

Categorical variables will be summarized using counts (n) and percentages (%) and will be presented in the form “n (xx.x).” If a count is 0, 0% will be shown for the percentage. To ensure completeness, summaries for categorical and discrete variables will include all categories, even if no subjects had a response in a particular category.

Continuous variables will be summarized using mean, SD, minimum, maximum, median and number of subjects. The 25th and 75th percentiles will be provided for distributions that are known to be skewed. The mean, median, 25th percentile, 75th percentile, and confidence intervals (CI) will be reported to 1 more level of precision than the original observations, and the SD will be reported to 2 more levels of precision than the original observations. The minimum and maximum will be the same precision as the original data.

When p-values are provided, they will be rounded to 3 decimal places; p-values that round to “0.000” will be presented as “<0.001.” Unless otherwise stated, all statistical tests of treatment effects will be conducted at a 2-sided alpha level of 0.05.

All analysis will be performed using SAS® System version 9.3 or later.

Dates in listings will be displayed as yyyy-mm-dd (e.g., 2015-01-24).

In general, age will be calculated in years using the date of birth and the date of randomization as [(date of randomization – date of birth)]/365.25, rounded down to the next largest integer using the floor function. For any listing that includes screen failures, age will be labeled as age at screening and will be calculated in years using the date of birth and the date of Visit 1 as [(date of Visit 1 – date of birth)]/365.25, rounded down to the next largest integer using the floor function.

In order to present summaries by treatment group regardless of sequence, the following parameters will be summarized as described below: safety laboratory, vital signs, signs and symptoms of malabsorption, weight, BMI, and serum liposoluble vitamins A, D, E, and K. These endpoints will be summarized relative to the time of first dose on a given study treatment. All post-randomization measurements will be relative to the time of the first dose. For example, in the MS1819 treatment column, the measurement at first dose will be Visit 3 if a subject is randomized to the MS1819-PERT sequence, and Visit 6 if a subject is randomized to the PERT-MS1819 sequence.

4. ANALYSIS POPULATIONS

The following 3 analysis populations will be identified for this study:

4.1 Modified Intent-to-Treat Population

The modified intent-to-treat (mITT) population includes all randomized subjects who receive at least 1 dose of treatment and have at least 1 sufficient stool sample. A stool sample will be considered sufficient if the date and time associated with the second blue dye marker is recorded, indicating that the stool sample collection is complete. The mITT will be used for efficacy analyses. Subjects will be analyzed according to the treatment group to which they were randomized regardless of the actual treatment received, unless stated otherwise.

4.2 Per-Protocol Population

The per-protocol (PP) population is a subset of the mITT population and includes all mITT subjects without major protocol deviations that could impact the efficacy analyses. Subjects who are found to be <80% compliant with MS1819 will be excluded from the PP population. The PP population will be used as supportive to the mITT population.

Prior to database lock, the protocol deviations will be reviewed and the PP Population will be determined. Subjects will be included in the treatment sequence to which they were randomized regardless of the actual treatment sequence received.

4.3 Safety Population

The safety population, which will be used for all safety analyses unless stated otherwise, will include all randomized subjects who receive at least 1 dose of treatment. Subjects in the safety population will be analyzed according to the actual treatment received regardless of their randomized assignment.

5. STUDY SUBJECTS

5.1 Disposition of Subjects

The disposition of subjects will be summarized for all subjects screened in the study. The following disposition information will be summarized overall:

- The number of subjects screened.
- The number of subjects who failed screening and the reason for screen failure.

All percentages will use the number of screened subjects as the denominator.

The following disposition information will be summarized by treatment sequence for all subjects randomized in the study:

- The number of subjects randomized.
- The number and percentage of subjects in the mITT population, PP population, and safety population.
- The number and percentage of subjects who completed the first treatment period (through Visit 6)
- The number and percentage of subjects who withdrew from the first treatment period and the reason for withdrawal
- The number and percentage of subjects who completed the second treatment period (through Visit 9)
- The number and percentage of subjects who withdrew from the second treatment period and the reason for withdrawal
- The number and percentage of subjects who completed the study (through visit 10)
- The number and percentage of subjects who withdrew from the study and the reason for withdrawal

All percentages will use the number of randomized subjects as the denominator.

A data listing of subject disposition for all randomized subjects and a data listing of screen failures will also be provided.

5.2 Protocol Deviations

Protocol deviations will be identified on an ongoing basis by the study team and recorded on the protocol deviation case report form (CRF) page.

The number and percentage of subjects with:

- at least 1 protocol deviation;
- at least 1 major protocol deviation;
- at least 1 protocol deviation for each protocol deviation type

will be summarized for the mITT population by treatment sequence.

Protocol deviation type is selected on the CRF from the list noted in Appendix 13.3.

Line listings will be provided to the study team for the manual classification of major vs. minor protocol deviations and the AzurRx study team will confirm classification of major vs. minor at a data review meeting prior to database lock. Each major deviation will be categorized as either important or not important with respect to the effect on the primary endpoint analysis.

All subjects in the mITT population having a protocol deviation and the details for the protocol deviation will be identified in a subject-level data listing. The listings will include the date of the deviation, protocol deviation type, if it was IRB reportable, date reported to IRB, any noted comments, and the deviation corrective and preventative action (CAPA).

6. DEMOGRAPHIC AND OTHER BASELINE CHARACTERISTICS

Subject demographics and other baseline characteristics will be summarized by treatment sequence and overall descriptively for the mITT population. The demographic and baseline characteristic summaries will be used to describe the study population as well as to check for balance among the treatment groups.

Demographic data will include age, sex, race, and ethnicity. Age (years) will be calculated using the date of birth and the date of randomization, as described in Section 3.

Baseline characteristic data will include gastric acid suppression use at randomization, CFTR (cystic fibrosis transmembrane conductance regulator) modulator use at randomization (yes, no), name of pre-randomization PERT, pre-randomization PERT dose (lipase units/kg/day), weight, height, body mass index (BMI), and years since diagnosis of EPI. Pre-randomization PERT dose (lipase units/kg/day) will also be summarized by region.

Descriptive statistics (number of subjects, mean, SD, minimum, median, and maximum values) will be presented for continuous variables for each treatment sequence. For qualitative or categorical variables, the number and percentage of subjects within each category will be presented by treatment sequence.

Individual data for demographics, baseline characteristics, and medical history will be presented in the data listings for subjects in the mITT population. A data listing of any inclusion/exclusion criteria not met will also be presented for all screened subjects.

Partial missing dates will be imputed for the purposes of determining time since diagnosis of EPI as follows:

- For a partially missing diagnosis date where the day is missing, but the month and year are present, the day will be set to the first day of the month.
- For a partially missing diagnosis date where the day and the month are missing, but the year is present, the month and day will be set to January 1st.

Years since diagnosis of EPI will be calculated in years using the imputed diagnosis date and the date of randomization as [(date of randomization – diagnosis date)]/365.25, rounded to one decimal place.

7. MEASUREMENTS OF TREATMENT COMPLIANCE

Treatment compliance will be summarized for MS1819-SD in terms of mg/day using a compliance rate. Given that subjects were to take the dose associated with their pre-study PERT during treatment with PERT, detailed pill information was not collected and thus compliance rate for PERT will not be summarized.

The compliance rate for MS1819-SD will be calculated as:

$$[\text{Actual Dose mg/day} / \text{Expected Dose mg/day}] * 100$$

The actual dose (mg/day) a subject received will be calculated as:

$$[(\text{number pills dispensed} - \text{number of pills returned}) * 140 \text{ mg}] / \text{number of actual study days on MS1819-SD},$$

where the number of actual study days on MS1819-SD is calculated as:

$$((\text{date/time of last MS1819-SD dose} - \text{date/time of first MS1819-SD dose}) / 86400) + 1.$$

The expected dose for MS1819-SD is 2240 mg/day.

Treatment compliance will be summarized by each study period and overall for MS1819-SD using descriptive statistics.

As described in Section 4.2, subjects found to be <80% compliant with MS1819-SD will be excluded from the PP population.

Individual data for study drug (number of pills) dispensed and returned and treatment compliance will be listed for all subjects in the mITT population.

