## **7.4 Investigational Products Administered**

### **7.4.1 MS1819-SD Administration**

At the time of prescribing, the Investigator or delegated site staff will fill in a source document with the appropriate dosing instructions.

MS1819-SD doses will typically be fractionated as follows: 1/4 of the daily dosage at each 3 main meals, and 1/8 at each of the 2 snacks (eg, for 2240 mg/day will be fractionated as follows: 4 capsules of 140 mg with the morning, noontime, and evening meals; plus 2 capsules of 140 mg with the morning and evening snacks).

Please refer to [Table 2](#) for dosing guidance.

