**Table 2: MS1819-SD Typical Dosing Schedule**

	Dose: 2240 mg/day
Breakfast	4 x 140 mg capsules
Snack 1	2 x 140 mg capsules
Lunch	4 x 140 mg capsules
Snack 2	2 x 140 mg capsules
Dinner	4 x 140 mg capsules
Total	16 (140 mg) capsules/day

Note: Individual variations may occur as long as correct total daily dose is achieved.

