8.2 Extent of Exposure

Time on treatment (weeks) will be calculated as (date of last dose of study drug – date first dose of study drug + 1)/7. Time on treatment will be summarized by treatment group for each period using descriptive statistics for all subjects in the safety population.

The date and time of the first and last dose of each study period will be presented in a data listing for all subjects in the safety population.

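### SAP 7 adds a whole day to clock-time exposure, so full adherence to the five-times-daily MS1819-SD schedule scores about 95–98% over 21 days and the 80% per-protocol cut-off sits at about 81–85%

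*SAP*

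**What the plan says.** - **Rate.** SAP 7 defines compliance as actual mg/day over expected mg/day, times 100. Actual mg/day is capsules dispensed minus capsules returned, times 140 mg, divided by the days on MS1819-SD. "The expected dose for MS1819-SD is 2240 mg/day".
- **Days on drug.** The text introduced by "where the number of actual study days on MS1819-SD is calculated as" takes the date/time of the last dose minus the date/time of the first, divides by 86400 and adds 1. The divisor is the number of seconds in a day, so this is exact elapsed time plus one full day.
- **Use.** SAP 4.2: "Subjects who are found to be <80% compliant with MS1819 will be excluded from the PP population". SAP 7 repeats the rule.
- **Regimen.** Protocol 7.4.1 describes "4 capsules of 140 mg with the morning, noontime, and evening meals; plus 2 capsules of 140 mg with the morning and evening snacks". Protocol Table 2 totals this as "16 (140 mg) capsules/day" and adds: "Individual variations may occur as long as correct total daily dose is achieved".
- **Exposure elsewhere.** SAP 8.2 computes weeks on treatment from calendar dates: "date of last dose of study drug – date first dose of study drug + 1)/7". It also says that the date and time of the first and last dose in each period will be listed, so clock times are available.

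**The concern.** Adding one to a difference of calendar dates is the usual inclusive count. With date/times it is right only when there is one dose a day at a fixed hour: n doses span n − 1 elapsed days, and adding 1 restores n. With five intakes a day, most of the last day is already inside the elapsed time, and the formula then adds another whole day.

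Two things are at stake. The compliance summary understates delivery of the 2240 mg/day under test. The exclusion threshold applied also differs from the one pre-specified, and it shifts with period length and with the hours of the first and last dose, none of which measures adherence. Partial end days are to be expected: MS1819-SD is dispensed at a clinic visit (Protocol 8.2.1), and the switch happens whenever the second dye marker passes (Protocol 8.3).

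**Working it through.** **The plan's own figure.** (3 × 4 + 2 × 2) capsules × 140 mg = 16 × 140 = 2240 mg/day. This reproduces.

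**Direction of the error.** Write the time from first to last dose as k whole days plus a fraction f, with 0 ≤ f < 1. The formula expects 16(k + f + 1) capsules. For regular intake:

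- if f > 0, at most 16k + 16 capsules are due, which is less than 16(k + f + 1);
- if f = 0, 16k plus the final intake of 2 or 4 are due, which is less than 16(k + 1).

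A regular patient with no missed capsule and an exact count therefore scores below 100%, whatever the meal times.

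**Size.** Score at full adherence = capsules due ÷ [16 × (elapsed days + 1)]. Effective cut-off = 80% ÷ that score. The documents give no meal times, so every time below is an assumption.

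*Worked example: breakfast 08:00, dinner 18:30 (10.5 h = 0.4375 day), 21 calendar days.*

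| First → last dose | Capsules due | Formula expects | Score | Effective cut-off |
|---|---|---|---|---|
| Breakfast → dinner | 21 × 16 = 336 | 16 × 21.4375 = 343 | 98.0% | 81.7% |
| Dinner → breakfast | 19 × 16 + 4 + 4 = 312 | 16 × 20.5625 = 329 | 94.8% | 84.4% |

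The denominator is too large by 7/16 = 0.44 day in the first row and by 17/16 = 1.06 days in the second.

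*Range: first intake 07:00–09:00, last intake 18:00–22:00, all combinations of starting and stopping intake.*

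| Calendar days | Score at full adherence | Effective cut-off |
|---|---|---|
| 14 | 91.7–97.4% | 82.1–87.2% |
| 21 | 94.6–98.2% | 81.4–84.6% |
| 31 | 96.3–98.8% | 81.0–83.0% |

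The top of the 14-day row comes from 09:00 and 18:00 with an evening start and a breakfast stop: due 12 × 16 + 8 = 200; formula 16 × (14 − 0.375) = 218; 200/218 = 91.7%; 80/0.917 = 87.2%. About 14 days is the shortest first period that the schedule allows: admission on Day 10 (Day 17 − 7), second marker given on confinement Day 4 (Day 13), then passed.

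**In capsules.** In the breakfast-to-dinner example, a true 80% is 0.80 × 336 = 268.8, so 269 capsules. The formula requires 0.80 × 343 = 274.4, so 275. Only a patient who used 269 to 274 capsules changes status.

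**Alternatives, at 21 days.**

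- Capsules due between first and last dose as denominator: full adherence scores 100% and the cut-off is 80% for any start and stop.
- Date/times without the added day: with 09:00 and 18:00, 336/(16 × 20.375) = 103.1% from breakfast to dinner and 312/(16 × 19.625) = 99.4% from dinner to breakfast. The cut-off is 77.6% to 80.5%.
- Calendar dates plus one, as in SAP 8.2: 100% for whole end days, but 312/336 = 92.9% for an evening start and breakfast stop, giving a cut-off of 86.2%.

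**The case against.** The arithmetic is hard to dispute, but four arguments limit it, and most of each stands.

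1. **A reader might infer that nobody can reach 100%.** The documents do not support that. The numerator is dispensed minus returned, so lost or unreturned capsules count as taken; in the worked example 7 or 17 of them cancel the understatement. The protocol also allows the daily split to vary. A patient who takes a full day's dose on both end days, and finishes on the last day at an earlier hour than the first dose, exceeds 100%. The error in the denominator runs one way; the net rate need not.
2. **The shifted cut-off is not a fixed number.** It depends on assumed meal times, period length and the intakes at each end. For the planned three weeks the shift is about 1 to 5 points. The 14-to-31-day range is not a bound either: an early stop, or a second period shortened by the visit windows, moves the cut-off further.
3. **A reader might infer that fully adherent patients who stop early are wrongly lost from the analysis.** The formula can indeed score them below 80%. The consequence is slight. The per-protocol set is a subset of mITT, which requires a sufficient stool sample, so a patient who stops in period 1 before any collection is outside both sets under any formula. One who stops early in period 2 has no MS1819-SD CFA, and exclusion removes only an unpaired PERT value.
4. **The rate is not the only evidence on adherence.** Capsules dispensed and returned and dose date/times are listed, time on treatment is summarised separately, and study drug taken at each meal and snack is recorded during confinement.

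What remains is that a pre-specified exclusion rule is applied to a rate that is wrong as written. Having the raw counts in listings does not correct the per-protocol set.

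**Conclusion.** The formula in SAP 7 is wrong for this regimen. With regular intake and an exact capsule count it overstates days on drug by roughly 0.4 to 1.1 days. Over 21 days full adherence then scores about 95–98%, and the nominal 80% cut-off corresponds to true adherence of about 81–85%; the cut-off reaches about 87% for a first period of about 14 days with an evening start and a breakfast stop. These figures rest on assumed intakes between 07:00–09:00 and 18:00–22:00. That a regular patient with an exact count scores below 100% does not depend on them.

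The effect is confined to the MS1819-SD compliance summary and membership of the per-protocol set. A reader might infer that the noninferiority result is at risk. The documents do not support that: SAP 9.2.1 bases the primary analysis on mITT, SAP 4.2 gives the per-protocol set a supportive role, and with about 38 patients planned few, if any, are likely to fall in the narrow band that changes status. The point is minor.

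**What to change.** In SAP 7, compute compliance as capsules taken (dispensed minus returned) divided by capsules expected. Expected capsules are 16 for each full calendar day between the end days. On the first and last dosing days, count the Table 2 intakes at or after the recorded first dose time and at or before the recorded last dose time. Table 2 has no clock times, so the SAP must state nominal intake times and say how a recorded time is matched to one; matching to the nearest would keep a slightly late breakfast from dropping out of the count. Apply the 80% rule in SAP 4.2 to this figure.

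If mapping to clock times is not wanted, drop the added day from the date/time formula. Under the same assumptions full adherence then scores about 99–103% at 21 days, with a cut-off of about 78–80.5%. Copying the calendar-date count from SAP 8.2 is the weaker choice, because partial end days would still count as whole days.

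The cost is one formula, a little more programming and a stated convention for intake times. No new data are needed.

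### The SAP's MS1819 compliance rate measures dosing intensity up to the last dose taken, so the below-80% per-protocol exclusion generally misses a patient who doses fully and then stops for good

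*SAP*

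**What the plan says.** SAP Section 7 defines the compliance rate as actual mg/day over expected mg/day, and states: "The expected dose for MS1819-SD is 2240 mg/day". The numerator of the actual dose is "number pills dispensed" minus pills returned, times 140 mg. The divisor is introduced by "where the number of actual study days on MS1819-SD is calculated as" and is the difference between "date/time of last MS1819-SD dose" and "date/time of first MS1819-SD dose", in days, plus 1.

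The rate has one decision attached to it. SAP 4.2 states: "Subjects who are found to be <80% compliant with MS1819 will be excluded from the PP population". Section 7 repeats it: "subjects found to be <80% compliant with MS1819-SD will be excluded from the PP population". SAP 4.2 also removes patients with major protocol deviations that could affect efficacy, but it sets no minimum duration of exposure.

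The Protocol synopsis limits the PP set to patients who complete both periods. Protocol 10.3 and SAP 4.2 do not repeat that condition, SAP 1 gives the SAP precedence over the protocol, and SAP 11.1 does not list the omission as a change.

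**The concern.** A compliance threshold for a PP set is normally meant to identify patients who did not receive the assigned treatment adequately over the period being assessed. Because this divisor ends at the patient's own last dose, permanent stopping shortens the numerator and the divisor together and leaves the ratio nearly unchanged. The rule responds to doses missed before the last dose and hardly at all to doses never taken after it. It can exclude a patient with a short interruption and retain one who was off MS1819 for most of the period.

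At stake is the supportive PP analysis of the noninferiority comparison (SAP 9.2.1.1). A patient who stops MS1819 before confinement, is admitted anyway and completes the collection contributes a coefficient of fat absorption (CFA) analysed by randomized treatment, that is, as an MS1819 value. The rule in SAP 9.2.1 that discards a CFA after a treatment switch covers only switches during the confinement. A stopper with no MS1819 collection can also remain in PP on a PERT value alone, because SAP 4.1 asks for only one sufficient stool sample.

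**Working it through.** **Expected dose.** Protocol Table 2 gives "16 (140 mg) capsules/day": 3 meals x 4 + 2 snacks x 2 = 16 capsules, and 16 x 140 mg = 2240 mg/day. The SAP's figure reproduces exactly.

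**Formula for a permanent stop.** Take a patient who doses fully through Day d, stops for good and returns the rest. Let h be the hours between the first and last dose of a day. The documents do not give h; 10 to 12 is assumed.

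- Capsules used: 16d
- Divisor: (d - 1) + h/24 + 1 = d + h/24
- Rate: 100 x (16d x 140) / [(d + h/24) x 2240] = 100 x d / (d + h/24)

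Example, Day 10 with h = 12: 10/10.5 = 95.2%.

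The last column divides the same intake by a planned 21-day period (16 x 21 = 336 capsules).

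| Last dose on day | SAP rate, h = 10 | SAP rate, h = 12 | Intake over 21 days |
|---|---|---|---|
| 1 | 70.6% | 66.7% | 4.8% |
| 2 | 82.8% | 80.0% | 9.5% |
| 3 | 87.8% | 85.7% | 14.3% |
| 5 | 92.3% | 90.9% | 23.8% |
| 10 | 96.0% | 95.2% | 47.6% |
| 14 | 97.1% | 96.6% | 66.7% |
| 16 | 97.5% | 97.0% | 76.2% |
| 17 | 97.6% | 97.1% | 81.0% |
| 21 | 98.1% | 97.7% | 100% |

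On the 21-day divisor, every stop up to Day 16 falls below 80%.

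**Very early stops.** The rate is below 80% only when d < h/6. At h = 12 that is Day 1 only; at h = 14, Day 2 also falls below (77.4%). If the first dose is at dinner on Day 1 (4 capsules that day, last dose at dinner), the rate is (d - 0.75)/d: 75.0% for Day 3, 81.2% for Day 4, and above 90% only from Day 8 (90.6%). These early failures arise because 1 is added to a date/time difference; the formula does not register the untreated days.

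**Interruption with resumption.** Missing 4 full days within 21 gives 17/21.5 = 79.1% (h = 12) or 17/21.42 = 79.4% (h = 10), so the patient is excluded. Missing 3 days gives 18/21.5 = 83.7%, and the patient stays.

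**Sensitivity to period length.** Visits 6 and 9 each carry a 7-day window either side, so take 21 - 7 = 14 to 21 + 7 = 28 days. A Day 5 stop is then 5/14 = 35.7% to 5/28 = 17.9%, and a Day 10 stop is 10/14 = 71.4% to 10/28 = 35.7%. Both stay below 80% throughout. A Day 14 stop does not: it is complete in a 14-day period.

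**Unreturned capsules.** These count as taken. If 336 capsules were dispensed (assumed; no dispensed quantity is stated), a Day 5 stopper returning none would score 336/(16 x 5.5) = 382%.

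**The case against.** The strongest reply is that the reach is narrow and other controls exist. Much of this stands.

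- **Few patients are affected.** For someone still dosing through the collection, the last dose falls close to its end and the two divisors nearly agree. A stopper who leaves before confinement has no MS1819 CFA, and none is imputed. Such a patient informs the PP treatment difference only through between-patient information.
- **Manual review can act.** SAP 5.2 has deviations classified before database lock and major ones rated for effect on the primary endpoint. Non-compliance with study treatment is a deviation type in SAP 13.3, and doses during confinement are recorded at every meal and snack. This is a real safeguard, but a discretionary one in an open-label trial, exercised with a listing that shows the stopper as over 90% compliant.
- **The synopsis condition.** Requiring both periods would remove stoppers with only a PERT value. It would not clearly remove one who attends both confinements, since SAP 5.1 counts completion through Visits 6 and 9.
- **The rate is labelled mg/day.** That is fair as a measure of intensity. The fault lies in using an intensity measure as the PP criterion.

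A reader might infer that the compliance table hides short exposure from the safety assessment. It does not: SAP 8.2 summarizes time on treatment by treatment and period and lists first and last dose times, and SAP 5.1 tabulates withdrawals by period with reasons. A reader might also expect rates of several hundred percent to pass unnoticed. That needs an assumed supply and no returns, whereas the protocol requires return and reconciliation of blisters and the SAP lists counts by subject.

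**Conclusion.** The point holds in a limited form. For permanent stopping after the first few days, the SAP rate stays above 80% and usually above 90%, so the numeric PP rule generally does not flag it. A stop at Day 5 or Day 10 scores about 91-92% or 95-96%, only a few points below a 21-day completer. The rule does detect interruptions of about 4 days followed by resumption, and may detect stops on Days 1-2, or Day 3 with a dinner start.

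Two stronger readings are not supported. One is that the plan cannot detect stopping at all: the earliest stops can fail the threshold, and deviation review remains. The other is that the noninferiority conclusion is compromised: the mITT analysis is primary, and the PP analysis changes materially only if a patient stops MS1819 before confinement yet completes that period's collection. If such a patient has gone back to PERT, the value would tend to pull the difference toward zero, which favours noninferiority given the expected -8%. If the patient takes no enzyme, the pull may be the other way. The documents do not allow the number of such patients, or the shift in the estimate, to be calculated.

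The percentages assume full dosing until the stop, return of all unused capsules and 10-12 hours of daily dosing. The 21-day comparison is illustrative, because actual period length varies with the visit windows.

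**What to change.** In SAP 4.2 and 7, base the below-80% rule on MS1819 capsules used divided by the days from first MS1819 dose to the end of that period's stool collection (date and time of the second marker). If MS1819 was stopped and no collection was completed, use the planned 3-week period. State whether the extra day is still added. Keep the current rate as a separate summary of adherence while on treatment.

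Before PP status is fixed, query any rate well above 100% against the accountability records. Simply declaring unreturned capsules unknown would leave PP status undefined.

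The cost is a few sentences, settled before database lock. Dose dates and times, second-marker times and capsule counts are already collected. Two drawbacks remain: a few more patients may leave the PP set, and rates on the planned 3-week divisor are not strictly comparable with those on the actual one.
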